10. EFFICACY ANALYSIS

The efficacy analyses will be based on the ITT population, and analyses of the primary efficacy endpoint will also be provided using the PP population. Statistical comparisons between apremilast 30 mg BID and placebo will be made for the primary endpoint. No inferential testing for statistical significance will be performed for the other endpoints. The statistical test will be two-sided at the significance level of $\alpha = 0.10$, and the corresponding p-values and two-sided confidence intervals (CIs) for point estimates will be presented. A subject data listing of efficacy data will be provided.

10.1. Multiplicity

Planned statistical test will be conducted for the primary efficacy endpoint. Secondary efficacy endpoints will be tested without multiplicity adjustment, therefore, other than the primary efficacy endpoint, nominal 2-sided p-value will be computed as a measure of the strength of the association between the endpoint and the treatment effect rather than formal tests of hypotheses.

10.2. Analysis of Primary Efficacy Endpoint

The primary efficacy endpoint which is achieving a PPPASI-50 response at Week 16 will be analyzed using a chi-square test at the two-sided 0.10 significant level. The two-sided 90% CI for the treatment difference of the PPPASI-50 response rate will be provided. The two-sided 95% CI will also be provided for reference. Missing values at Week 16 will be imputed using non-responder imputation (NRI) as the primary method, by which a subject without sufficient data for the response determination will be considered a non-responder. Last observation carried forward (LOCF) method imputing the last post-baseline observation to missing data at the time point under consideration will be applied as sensitivity analysis. In addition to the primary analysis using the ITT population, an analysis using the PP population will be provided.

To support the primary analysis, sensitivity analysis using the Cochran-Mantel-Haenszel (CMH) test stratified by the randomization stratification factors [PPPASI total score range (≤ 20 , 21-30, ≥ 31) and focal infection status (Yes, No)] will be conducted. The two-sided p-values (nominal) from the CMH test, the adjusted treatment difference in proportion using the weighted average of the treatment differences across the strata with the CMH weights, along with the associated two-sided 95% CIs using a normal approximation to the weighted average will be provided.

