## Statistical Methods

### Efficacy

The primary analysis of the proportion of subjects who achieve a PPPASI-50 at Week 16 will be carried out using a chi-square test. A result will be expressed as number and percentages of subjects who achieve a PPPASI-50 and associated 90% confidence intervals (CIs) and p-values. The statistical test will be conducted at the  $\alpha = 0.10$  (two-sided) level.

For the exploratory purpose, secondary and exploratory efficacy endpoints including but not limited to PPPASI, PPSI, PGA and SRO, will be tested without multiplicity adjustment, therefore p-values for those endpoints will be regarded as nominal.

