## 7.5. Method of Treatment Assignment

At Visit 2, subjects who meet eligibility criteria will be randomized using a permuted block randomization in parallel with 1:1 ratio to receive either apremilast 30 mg BID or placebo, using a centralized IRT. Eligible subjects will be stratified according to a subject's rounded PPPASI score ( $\leq 20$  /  $21-30$  /  $\geq 31$ ) at randomization, and whether a subject has or not any focal infection at randomization (yes/no). Designated research personnel at the investigational sites will be assigned password protected, coded identification numbers, which give them authorization to enter the IRT to randomize subjects.

The system will present a menu of questions by which the research center personnel will identify the subject and confirm eligibility. When all questions have been answered, the IRT will assign a randomization identification number.

Confirmation of the randomization will be sent to the investigational site, Amgen, and/or its representative. During the study visits, the pharmacy or authorized study personnel at the investigational site will dispense coded IP kits in accordance with the randomization identification number assigned by the IRT.

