#### **9.6.1.1. Primary Efficacy Endpoint - (Weeks 0 - 16)**

The primary efficacy endpoint of the proportion of subjects receiving apremilast 30 mg BID or placebo who achieve a PPPASI-50 at Week 16 from baseline will be evaluated.

The primary efficacy endpoint will be analyzed using a chi-square test. The testing will be conducted at the two-sided 0.10 significant level and the two-sided 90% CI for the treatment difference of the PPPASI-50 response rates will be provided. The two-sided 95% CI will also be provided for reference. The primary missing data handling approach for PPPASI-50 responder will be nonresponder imputation (NRI), by which a subject without sufficient data for the response determination will be considered a nonresponder. Sensitivity analysis using the PP population and/or the other missing data handling approach [eg, last observation carried forward (LOCF) method] will be performed and the Cochran-Mantel-Haenszel (CMH) test stratified by the randomization stratification factors [PPPASI total score range ( $\leq 20$  score, 21-30 score,  $\geq 31$  score) and focal infection status (Yes, No) at baseline] will be conducted to support the primary analysis.

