#### **9.6.1.2. Secondary Efficacy Endpoints - (Weeks 0 - 16)**

Descriptive statistics will be presented for all secondary endpoints in [Table 2](#). Specifically, for continuous endpoints, descriptive statistics (n, mean, standard deviation, median, minimum, and maximum) for baseline, Week 16 and Week 16 change from baseline will be provided. Binary endpoints will be summarized with frequency tabulations.

Treatment comparisons between the apremilast 30 mg BID and placebo will be performed for the secondary endpoints. Continuous efficacy endpoint will be analyzed using the analysis of covariance (ANCOVA) model adjusted for PPPASI total score range ( $\leq 20$  score, 21-30 score,  $\geq 31$  score) and focal infection status (yes, no) at baseline as factors, and the associated baseline value as covariate, while binary endpoints will be evaluated using the CMH test previously described for the primary endpoint. The primary missing data handling approach for continuous endpoint will be multiple imputation (MI).

Secondary efficacy endpoints will be tested without multiplicity adjustment, therefore the p-value for those endpoints will be regarded as nominal. For secondary efficacy endpoints, the two-sided 95% CI will be provided.

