10.3.1. Binary Variables

The binary variables for secondary and exploratory endpoints include:

Subjects achieving a

- PPPASI-50 response
- PPPASI-75 response

CC-10004 (Apremilast)

Statistical Analysis Plan. Protocol CC-10004-PPP-001

- PGA score of cleared (0) or minimal (1)
- PGA score of cleared (0) or minimal (1) with at least a 2-grade improvement
- Modified PPPASI-50 response
- Modified PPPASI-75 response

For these binary endpoints, proportion at each visit will be displayed along with 95% CIs. The treatment difference between apremilast 30 mg BID and placebo will be compared using difference in proportions and CMH test adjusting for the stratification factor. The two-sided p-values (nominal) from the CMH test, the adjusted treatment difference in proportion using the weighted average of the treatment differences across the strata with the CMH weights, along with the associated two-sided 95% CIs using a normal approximation to the weighted average will be provided. The two-sided 95% CI based on the Clopper-Pearson method will be provided for un-adjusted difference. Missing values will be imputed using NRI. For the exploratory purpose, LOCF will be applied to the data of the placebo-controlled phase.

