10.3.2. Continuous Variables

The continuous variables for secondary and exploratory endpoints in placebo-controlled phase include the following:

- AUC for PPPASI total score from baseline through Week 16
- PPPASI total score change from baseline at Week 16
- AUC for PPSI total score from baseline through Week 16
- PPSI total score change from baseline at Week 16
- AUC for modified PPPASI total score from baseline through Week 16
- Modified PPPASI total score change from baseline at Week 16
- Subject's assessment for PPP sign/finding (PPSI total score) at Week 16

The analysis of covariance (ANCOVA) model with treatment and stratification factor as the fixed effects, the associated baseline value as the covariate and multiple imputation (MI) method to impute the missing data will be applied. Within-group least-squares (LS) means, the associated standard error (SE), and treatment differences in LS means, the associated SE, and associated 2-sided 95% CIs and 2-sided p-values (nominal) will be derived from the model.

Missing value of at Week 16 will be imputed using the MI method ([SAS Institute Inc. 2015](#)) except for AUC. The SAS procedure MI will be used to impute missing scores to create M=100 complete data sets. The missing data patterns will be checked by treatment at baseline, and Week 2, 4, 6, 8, 10, 12, 14, and 16. If there are non-monotone missing patterns, following two separate imputation procedures will be used to complete the imputation process.

1. In the first step, the Markov Chain Monte Carlo (MCMC) method will be used to impute missing scores by treatment to create M=100 imputed data sets with monotone missing patterns. The minimum and maximum values for imputation will correspond to the lowest and the highest scores. The seed will be set at random, a single chain will be used to produce imputations. In case there are convergence issues, a simple model will be used to impute the

CC-10004 (Apremilast)

Statistical Analysis Plan. Protocol CC-10004-PPP-001

missing scores by treatment, with further simplification by dropping both treatment and stratification factor in imputation model if necessary.

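### The one formal test ignores the six randomisation strata; promoting the already planned CMH test would be a cheap, modest efficiency gain, with a small loss if the strata carry no information

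*SAP*

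**What the plan says.** **Randomisation.** Protocol 7.5: "Eligible subjects will be stratified according to a subject's rounded PPPASI score" (20 or below, 21 to 30, 31 or above) and by focal infection yes/no. SAP 4.3 agrees. That makes 3 x 2 = 6 strata, filled by permuted blocks; I found no block size in the text available to me.

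**Primary test.** The Protocol Summary says the analysis "will be carried out using a chi-square test". Protocol 9.6.1.1: "The primary efficacy endpoint will be analyzed using a chi-square test". SAP 10.2: the endpoint "will be analyzed using a chi-square test at the two-sided 0.10 significant level". All three agree, and the sample size is built on the same test.

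**Stratified version.** Protocol 9.6.1.1 and SAP 10.2 also plan a CMH test of this endpoint by the randomisation factors, as supportive analysis; the SAP labels its p-value nominal. SAP 10.2 adds a CMH-weighted difference, with "associated two-sided 95% CIs using a normal approximation to the weighted average will be provided". No variance formula is named, and no 90% interval is planned for the weighted difference.

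**Other endpoints.** Protocol 9.6.1.2: "binary endpoints will be evaluated using the CMH test previously described for the primary endpoint". SAP 10.3.1 has binary endpoints "compared using difference in proportions and CMH test adjusting for the stratification factor". SAP 10.3.2 uses an ANCOVA "model with treatment and stratification factor as the fixed effects", an MMRM with the same factor, and stratified log-rank and Cox analyses. DLQI and EQ-5D are only summarised, with no model or p-value.

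**The concern.** Balancing on a factor and then leaving it out of the test puts between-stratum variation into the error term. If the strata predict response, the unstratified chi-square becomes conservative: its true size drops below 0.10 and it gives up power that a stratified test keeps. The trial has 86 subjects and is planned at 80% power, and the stratified test is already specified, so the power can be had without new data.

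A second detail sits beside it. Strata average 86/6, about 14 subjects, or about 7 per arm. At that size the choice of variance for the CMH-weighted difference affects coverage, and the SAP leaves it open in both 10.2 and 10.3.1.

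**Working it through.** **1. The plan's own figure.** Inputs from Protocol 9.3 and SAP 4.4: 45% vs 20%, two-sided 0.10, 86 subjects. Protocol 4.1 gives 43 per arm.

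- Pooled SD term: sqrt(2 x 0.325 x 0.675) = 0.6624. Unpooled: sqrt(0.45 x 0.55 + 0.20 x 0.80) = 0.6384.
- n per arm = (1.645 x 0.6624 + 0.842 x 0.6384)^2 / 0.25^2 = 42.3, so 43.
- Power at 43 per arm = Phi[(0.25 x sqrt(43) - 1.645 x 0.6624) / 0.6384] = Phi(0.861) = 80.5%.

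Exact enumeration of the uncorrected chi-square gives 80.8%. The stated 80% reproduces.

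**2. Comparing the two tests.** Both refer to chi-square on 1 df at 0.10 (critical value 1.645^2 = 2.706). For stratum k, with arm sizes n_A and n_B, total n, m responders and a responders on apremilast:

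CMH = [sum(a - n_A m/n)]^2 / sum[n_A n_B m (n - m) / (n^2 (n - 1))].

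Trials of 86 were simulated with permuted blocks within six strata. Stratum effects were additive on the logit scale, calibrated so that marginal rates stayed at 20% and 45% (or 20% and 20% for size). **Assumed, because the documents do not give them:** block size, stratum shares (seven patterns, including a 90/10 focal split) and the odds ratio (OR) per level. There were 100,000 trials per scenario.

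CMH minus chi-square power, in points, with blocks of 4:

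| OR per level | Range over share patterns |
|---|---|
| 1 on both (no prognosis) | -0.9 to -0.4 |
| 1.5 on one factor | -0.9 to 0.0 |
| 1.5 on both | -0.3 to +0.2 |
| 2 on one factor | -0.7 to +1.0 |
| 2 on both | +0.6 to +1.5 |
| 3 on one factor | -0.3 to +3.3 |
| 3 on both | +2.5 to +3.9 |

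For shares 35/40/25 by 60/40, chi-square vs CMH power is 81.2 vs 80.7% (no prognosis), 82.3 vs 83.5% (OR 2 on both) and 82.9 vs 86.4% (OR 3 on both).

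**3. Sensitivity to the settings.** With no prognosis, equal strata and blocks of 2 the loss is 0.3 points. With shares 60/20/20 by 90/10 and blocks of 8 it is about 1.2 to 1.4, and CMH power is about 80%. At the other end, OR 5 on both factors gives about +5 to +6.5.

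**4. True size at 20% vs 20%.**

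| | Chi-square | CMH |
|---|---|---|
| No prognosis | 0.104-0.105 | 0.098-0.103 |
| OR 2 on both | 0.091-0.098 | 0.098-0.103 |
| OR 3 on both | 0.076-0.089 | 0.098-0.103 |

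The CMH range is over all scenarios.

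**5. Coverage of the nominal 95% interval for the CMH-weighted difference.** Summing simple per-stratum binomial variances gives 91.9-93.1%. The Sato variance gives 94.1-94.6%.

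**The case against.** **The plan is coherent as written.** Test and sizing agree throughout, and the chi-square after stratified randomisation is valid. A reader might infer an error, a contradiction or type I error inflation. The documents support none of these: prognostic strata push the size down, and the 0.104-0.105 without prognosis is small-sample discreteness. This stands.

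**The CMH result will be reported anyway.** True, so what remains is which result carries the formal test. A reader might also infer that PPPASI-50 is analysed by CMH up to Week 14 and then switched. It is not: CMH is run at Week 16 too. Nor does every other endpoint get an adjusted p-value, since DLQI and EQ-5D get none.

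**The gain is not established.** The documents give no prognostic strength. OR 3 on both factors is a 27-fold odds range (3 x 3 x 3); with equal strata it means placebo response from about 3% to 49%. PPPASI-50 is a percentage improvement from each subject's own baseline, so strong prediction by baseline PPPASI cannot be presumed. Gains above 1.5 points appear only at OR 3 or more. This limits the point to a modest one.

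**Focal infection may be rare.** Protocol 4.3 excludes subjects whose periodontitis, tonsillitis or sinusitis needs treatment as defined there. Under a 90/10 split with blocks of 4, 57-66% of simulated trials had a stratum with subjects in one arm only, which adds nothing to CMH. The cost is real but small: it is the 1.2 to 1.4 points above.

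**Conclusion.** The point holds as an efficiency improvement. The only formal test leaves out factors that the trial randomises on and that the SAP's other specified p-values use. Under the assumptions shown, the switch to CMH costs about 0.3 to 1.4 points of power if the strata are uninformative. It is close to neutral at weak prognosis, and gains about 0.5 to 1.5 points at OR 2 on both factors, about 2.5 to 4 at OR 3 on both, and more beyond that. CMH also holds its size near 0.10 where the chi-square drifts to about 0.08.

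These figures are illustrative. It would be tempting to read the ends of any one grid as bounds, but they move with block size, stratum shares and where the odds ratios stop. The documents fix none of these.

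The unnamed variance is a smaller gap that matters whichever test is primary: the simple choice gives about 92-93% coverage for a nominal 95% interval.

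**What to change.** Before the Week 16 unblinding:

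1. Make the CMH test, stratified by the randomisation factors as recorded in the IRT, the primary test at two-sided 0.10. Keep the unstratified chi-square as sensitivity analysis.
2. Report the CMH-weighted difference with a 90% CI (95% for reference), using a sparse-strata variance such as Sato. State that strata with subjects in only one arm do not contribute.
3. Amend the Protocol Summary (Statistical Methods), Protocol 9.6.1.1 and SAP 10.2 together. N=86 need not change; the sizing text can say that it rests on the unstratified test.

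**Cost.** Up to about 1 to 1.4 points of power if the strata are uninformative, a SAP revision, and a protocol amendment with IRB/EC written approval (Protocol 13.5). No new data or subjects.

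**If the chi-square stays primary:** name the Sato variance for the CMH-weighted intervals in SAP 10.2 and 10.3.1. This is a SAP wording change.

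**Wording note only:** SAP 10.4 refers to a primary analysis model with treatment, stratum and covariate terms, while SAP 10.2 specifies no such model. Changing the primary test does not resolve this, so the two sections need reconciling.

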10.3. Analyses of Secondary and Exploratory Efficacy Endpoints

The secondary efficacy endpoints will be tested without multiplicity adjustment, therefore, both secondary and exploratory endpoints analyses are described in this section.

10.3.1. Binary Variables

The binary variables for secondary and exploratory endpoints include:

Subjects achieving a

- PPPASI-50 response
- PPPASI-75 response

CC-10004 (Apremilast)

Statistical Analysis Plan. Protocol CC-10004-PPP-001

- PGA score of cleared (0) or minimal (1)
- PGA score of cleared (0) or minimal (1) with at least a 2-grade improvement
- Modified PPPASI-50 response
- Modified PPPASI-75 response

For these binary endpoints, proportion at each visit will be displayed along with 95% CIs. The treatment difference between apremilast 30 mg BID and placebo will be compared using difference in proportions and CMH test adjusting for the stratification factor. The two-sided p-values (nominal) from the CMH test, the adjusted treatment difference in proportion using the weighted average of the treatment differences across the strata with the CMH weights, along with the associated two-sided 95% CIs using a normal approximation to the weighted average will be provided. The two-sided 95% CI based on the Clopper-Pearson method will be provided for un-adjusted difference. Missing values will be imputed using NRI. For the exploratory purpose, LOCF will be applied to the data of the placebo-controlled phase.

10.3.2. Continuous Variables

The continuous variables for secondary and exploratory endpoints in placebo-controlled phase include the following:

- AUC for PPPASI total score from baseline through Week 16
- PPPASI total score change from baseline at Week 16
- AUC for PPSI total score from baseline through Week 16
- PPSI total score change from baseline at Week 16
- AUC for modified PPPASI total score from baseline through Week 16
- Modified PPPASI total score change from baseline at Week 16
- Subject's assessment for PPP sign/finding (PPSI total score) at Week 16

The analysis of covariance (ANCOVA) model with treatment and stratification factor as the fixed effects, the associated baseline value as the covariate and multiple imputation (MI) method to impute the missing data will be applied. Within-group least-squares (LS) means, the associated standard error (SE), and treatment differences in LS means, the associated SE, and associated 2-sided 95% CIs and 2-sided p-values (nominal) will be derived from the model.

Missing value of at Week 16 will be imputed using the MI method ([SAS Institute Inc. 2015](#)) except for AUC. The SAS procedure MI will be used to impute missing scores to create M=100 complete data sets. The missing data patterns will be checked by treatment at baseline, and Week 2, 4, 6, 8, 10, 12, 14, and 16. If there are non-monotone missing patterns, following two separate imputation procedures will be used to complete the imputation process.

1. In the first step, the Markov Chain Monte Carlo (MCMC) method will be used to impute missing scores by treatment to create M=100 imputed data sets with monotone missing patterns. The minimum and maximum values for imputation will correspond to the lowest and the highest scores. The seed will be set at random, a single chain will be used to produce imputations. In case there are convergence issues, a simple model will be used to impute the

CC-10004 (Apremilast)

Statistical Analysis Plan. Protocol CC-10004-PPP-001

missing scores by treatment, with further simplification by dropping both treatment and stratification factor in imputation model if necessary.

2. In the second step, the predictive mean matching method will be used to impute the remaining missing values for the 100 data sets with monotone missing patterns. The MONOTONE REGPMM statement will be used with a random seed. The missing values at each visit will be imputed based on treatment and previous visits. The number of closest observations to be used in the selection will be K=2.

After the completion of imputation, the same analysis method/model will be used to analyze the 100 complete data sets and the SAS procedure MIANALYZE will be used to combine the results for the statistical inferences.

Following continuous variables for secondary and exploratory endpoints will be summarized by time point. Change and percent change from baseline will be provided. The mixed-effect model for repeated measures (MMRM) will be applied for the endpoints; PPPASI and modified PPPASI, PPSI, and subject's VAS assessment for PPP symptoms. The MMRM model will use the change from baseline as the response variable and include treatment group, visit time, treatment-by-time interaction, and stratification factor as fixed effects, and the baseline value as a covariate. An unstructured covariance matrix will be used to model the correlation among repeated measurements. Within-group LS means and the associated SEs and 2-sided 95% CIs, treatment differences in LS means and the associated 2-sided 95% CIs and 2-sided p-values (nominal) will be derived from the MMRM model.

- PPPASI total score
- Individual PPPASI sub-score (Erythema, Pustules/Vesicle, Desquamation/Scale) change and percent change from baseline at each visit
- PPSI total score
- Subject's VAS assessment for PPP symptoms
- Modified PPPASI total score
- Modified PPPASI sub-score (Pustules, Vesicle)
- Subject's assessment for PPP sign/finding (PPSI total score)
- DLQI
- EQ-5D index value
- EQ-5D VAS

Analyses of time to PPPASI response during the placebo-controlled phase will use Kaplan-Meier method to estimate the median response time and its 2-sided 95% CIs. The stratified log-rank test will be used for calculating 2-sided p-values (nominal) for treatment comparison. The hazard ratio and 2-sided 95% CIs will be estimated using a stratified Cox model. For the time to PPPASI response, the baseline score will be included as covariate in the Cox model. The treatment comparison will only be conducted if appropriate. Kaplan-Meier curves for time to event endpoints will be provided.

CC-10004 (Apremilast)

Statistical Analysis Plan. Protocol CC-10004-PPP-001

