**Table 2: Study Efficacy Endpoints**

Endpoint	Name	Description	Timeframe
Primary	PPPASI: PPPASI-50 See Appendix B about PPPASI total score.	Proportion of subjects who achieve a PPPASI- 50 at Week 16.	Week 16
Secondary	PPPASI: PPPASI-50	Proportion of subjects who achieve a PPPASI- 50 at each visit.	By visit in double blind, placebo-controlled phase (except for baseline and Week 16)
	PPPASI: PPPASI-75	Proportion of subjects who achieve a PPPASI- 75 at each visit.	By visit in double blind, placebo-controlled phase (except for baseline)
	PPPASI total score	AUC.	Week 0-16
		Percent change from baseline.	By visit in double blind, placebo-controlled phase (except for baseline)
	PPSI total score See Appendix C about PPSI total score.	AUC.	Week 0-16
		Percent change from baseline.	By visit in double blind, placebo-controlled phase (except for baseline)

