4.2.4. Derivation of Efficacy Endpoints

The definition and derivation of efficacy endpoints are described below and in the appendices of the protocol. Change from baseline is calculated as post-baseline visit value - the baseline value. Percent change from baseline is defined as $100 \times \text{change from baseline}/\text{baseline value} (\%)$. Baseline definition for all efficacy endpoints is given in [Section 5.3](#). Handling of time points is described in [Section 5.4](#).

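### SAP 10.3.2 compares the arms on absolute change in PPPASI and PPSI total score and does not carry through the promised comparison on percent change, the declared secondary endpoint; SAP Section 15 reports no departure (minor)

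*SAP*

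**What the plan says.** **Declared endpoint.** Protocol Table 2 lists "Percent change from baseline" for PPPASI total score and for PPSI total score, by visit in the placebo-controlled phase. SAP Table 2 (Section 4.2.2) lists the same. Neither table has absolute change in these two scores as a secondary endpoint.

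**Definitions.** SAP 4.2.4 separates the two quantities. For the first: "Change from baseline is calculated as post-baseline visit value - the baseline value". For the second, the sentence that opens "Percent change from baseline is defined as" gives 100 times that change divided by the baseline value.

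**What is promised.** Protocol 9.6.1.2: "Treatment comparisons between the apremilast 30 mg BID and placebo will be performed for the secondary endpoints". Continuous endpoints are to have an ANCOVA with multiple imputation (MI) as the primary missing-data approach, and "For secondary efficacy endpoints, the two-sided 95% CI will be provided". SAP 10.1 adds a nominal two-sided p-value for endpoints other than the primary.

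**What is specified.** The ANCOVA list in SAP 10.3.2 contains "PPPASI total score change from baseline at Week 16" and the corresponding PPSI line. For the repeated-measures analysis, "The MMRM model will use the change from baseline as the response variable". Percent change appears in 10.3.2 only among the summaries by time point.

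**Declared departures.** SAP Section 15 states that nothing in the protocol's statistical section has been changed.

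**The concern.** An analyst who follows SAP 10.3.2 exactly will produce, for two declared secondary endpoints, a percent-change summary in each arm. There will be no treatment difference, CI or nominal p-value on that variable. The between-arm results reported for PPPASI and PPSI total score will be on a variable that neither endpoint table declares as secondary.

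What is at stake is traceability. The study report would either lack a comparison that the protocol promised or need an analysis that the SAP does not specify, while Section 15 tells the reader that plan and protocol agree.

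**Working it through.** **1. The plan's own figure, to bound the issue.** Inputs from SAP 4.4: rates 45% and 20%, two-sided alpha 0.10, power 80%, chi-square test. With pooled variance under the null:

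n per arm = [1.645 × √(2 × 0.325 × 0.675) + 0.842 × √(0.45 × 0.55 + 0.20 × 0.80)]² / 0.25² = [1.645 × 0.6624 + 0.842 × 0.6384]² / 0.0625 ≈ 42.3, rounded up to 43.

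This gives N = 86, with power 80.5% at 43 per arm. The stated size reproduces, and nothing below enters it.

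**2. Each endpoint in SAP Table 2 against SAP 10.3.1 to 10.3.3.**

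| Secondary endpoint | Between-arm analysis in the SAP |
|---|---|
| PPPASI-50 | CMH |
| PPPASI-75 | CMH |
| PPPASI AUC | ANCOVA |
| PPPASI percent change | none; absolute change modelled |
| PPSI AUC | ANCOVA |
| PPSI percent change | none; absolute change modelled |
| PGA change | none; shift table only |
| PGA 0/1 | CMH |
| PGA 0/1 with 2-grade improvement | CMH |
| VAS change | MMRM |

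Tally: 7 on the declared variable + 2 on another scale + 1 shift table only = 10. PGA change is the lesser gap, because its two responder endpoints are compared.

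**3. Could the word change be meant to include percent change?** SAP 4.2.4 gives the two terms different formulas. SAP 10.3.2 names both when it describes the summaries, then names only change as the MMRM response. On the SAP's own usage, the models are on absolute change.

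**4. The two scales are not interchangeable.** Percent fall = 100 × fall / baseline. For a 6-point fall in PPPASI:

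- baseline 12 (the minimum under inclusion criterion 5): 6/12 = 50%
- baseline 20: 6/20 = 30%
- baseline 31: 6/31 = 19%

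A difference in points cannot be read back as the declared percentage. This shows only that the variables differ.

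**5. Is percent change always defined?** For PPPASI yes, since eligible subjects have a baseline of at least 12. For PPSI the documents do not guarantee it. PPSI runs from 0 to 12 on a site chosen at screening, and no entry criterion sets a minimum. Criterion 6 requires a PPPASI pustule/vesicle score of at least 2 on palms or soles, which is not tied to the PPSI site. Any added PPSI analysis therefore needs a rule for a baseline of 0.

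**6. Other departures from Protocol 9.6.1.2 that Section 15 omits.** SAP 10.3.2 excepts the AUC endpoints from MI, whereas the protocol makes MI the primary approach for continuous endpoints. MMRM is not in Protocol 9.6.1.2. The SAP adds it alongside ANCOVA for PPPASI and PPSI, and makes it the only model for VAS change. SAP Table 2 lists VAS change as secondary. In Protocol Table 2 it appears to sit in the exploratory block; the table layout may account for that, so the label should be checked.

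**The case against.** The strongest reply is that the documents do cover the point. Protocol 9.6.1.2 names the ANCOVA, its factors and covariate, MI and a 95% CI for the secondary endpoints. SAP 10.1 promises nominal p-values, and Section 15 says that the protocol's analyses are unchanged. This stands in part. A reader might infer that no comparison on percent change is promised anywhere; that is wrong. The gap is that SAP 10.3.2, the operative text, does not carry the general promise through.

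A second reply is that the protocol itself speaks of change: its descriptive sentence says "for baseline, Week 16 and Week 16 change from baseline will be provided". That sentence governs summaries. The comparison sentence refers to the secondary endpoints, which Table 2 defines as percent change for these scores.

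Third, SAP Section 10 disclaims inferential testing beyond the primary endpoint. Sections 10.1 to 10.3 still specify nominal p-values, and the protocol's promise of a CI does not depend on testing.

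Fourth, baseline-adjusted absolute change is a standard and defensible choice, and PPPASI-50 and PPPASI-75 already compare the arms on percent thresholds at each visit. Both points stand. The first is why declaring the choice would be an acceptable minimum correction. The second does not reach PPSI, which has no responder endpoint.

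Three stronger readings are tempting and unsupported:

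- **That the scale could be picked after seeing results.** SAP Section 2 has the plan signed before Week 16 unblinding, and 10.3.2 fixes absolute change.
- **That the two scales would lead to different conclusions or power.** The documents give no means or standard deviations for either variable, so this cannot be shown.
- **That the primary result is affected.** It rests on the PPPASI-50 chi-square test, which is unchanged.

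**Conclusion.** The point holds as a minor mismatch between the declared endpoint and the specified analysis. For two of the ten secondary endpoints in SAP Table 2, the between-arm models use a variable other than the declared one. PPSI has no between-arm comparison on the percent scale; PPPASI has one only through its responder thresholds. PGA change has a shift table only. The statement in SAP Section 15 that nothing has changed is incorrect.

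The effect is confined to nominal, unadjusted secondary analyses. The conclusion rests on reading change in SAP 10.3.2 as SAP 4.2.4 defines it, and on taking the endpoint tables as the statement of what is secondary. The count of ten uses SAP Table 2, including VAS change.

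**What to change.** **SAP 10.3.2.** Add percent change from baseline at Week 16 in PPPASI total score and in PPSI total score to the ANCOVA list, with the same factors and covariate. Derive it as 100 × (Week 16 score − baseline) / baseline within each of the 100 imputed data sets. State that a subject with a PPSI baseline of 0 is excluded from the PPSI percent-change analysis, and report how many there are. Keep the absolute-change ANCOVA and the MMRM as supportive.

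**SAP Section 15.** List what then still departs from Protocol 9.6.1.2:

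1. Percent change before Week 16 is descriptive only.
2. PGA change is described by shift table and compared only through its two responder endpoints.
3. The AUC endpoints are excepted from MI.
4. MMRM is added for PPPASI and PPSI, and is the only model for VAS change; check the VAS label in Protocol Table 2.

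**Cost.** Two list lines, a derivation sentence, the PPSI rule and a four-item Section 15. The downside is two extra nominal ANCOVAs, and PPSI percentages are coarse at low baselines (one point is 25% at a baseline of 4 and about 8% at 12). No new data or imputation model is needed, and the primary analysis is untouched.

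**Minimum alternative.** If the sponsor prefers absolute change, state in Section 15 that the comparison for these two scores is on absolute change and that percent change is descriptive. The PGA, AUC and MMRM items should be declared in either case.
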